5.2.6.2.2 AE reporting to the sponsor and timelines

The investigator must report SAEs, AESIs, and non-serious AEs which are relevant for the reported SAE or AESI, on the BI SAE form via fax immediately (within 24 hours) to the sponsor's unique entry point (country specific contact details will be provided in the ISF). The same timeline applies if follow-up information becomes available. In specific occasions, the investigator could inform the sponsor upfront via telephone. This does not replace the requirement to complete and fax the BI SAE form.

With receipt of any further information to these events, a follow-up SAE form has to be provided. For follow-up information the same rules and timeline apply as for initial information. All (S)AEs, including those persisting after individual patient's end of trial must be followed up until they have resolved, have been assessed as "chronic" or "stable" , or no further information can be obtained.

5.2.6.2.3 Pregnancy

In rare cases, pregnancy might occur in a clinical trial. Once a patient has been enrolled in the clinical trial and has taken trial medication, the investigator must report any drug exposure during pregnancy in a trial participant immediately (within 24 hours) by means of Part A of the Pregnancy Monitoring Form to the sponsor's unique entry point.

[figure not shown]
[figure not shown]
[figure not shown]
The outcome of the pregnancy associated with the drug exposure during pregnancy must be followed up and reported to the sponsor's unique entry point on the Pregnancy Monitoring Form for Studies (Part B).

[figure not shown]
[figure not shown]
The ISF will contain the Pregnancy Monitoring Form for Studies (Part A and B).

As pregnancy itself is not to be reported as an AE, in the absence of an accompanying SAE and/or AESI, only the Pregnancy Monitoring Form for Studies and not the SAE form is to be completed. If there is an SAE and/or AESI associated with the pregnancy an SAE form must be completed in addition.

5.2.6.2.4 Exemptions to SAE reporting

For this study there are no exemptions to SAE reporting.

5.5 BIOBANKING

N/A

5.6 OTHER ASSESSMENTS

N/A

5.7 APPROPRIATENESS OF MEASUREMENTS

The safety assessments are standard, are accepted for evaluation of safety and tolerability of a SC administered drug, and are widely used in clinical trials. The pharmacokinetic parameters and measurements outlined in [Section 5.3](#) are generally used assessments of drug exposure. The biomarker parameters outlined in [Section 5.4](#) are of exploratory nature only.

Information about race should be obtained from all study participants as allowed by local regulations. This is because the prevalence and characteristics of AD may differ between patients of different racial origin. It will thus be worthwhile to assess if patients of different race will respond differently to the study treatment.

6. INVESTIGATIONAL PLAN

6.1 VISIT SCHEDULE

All patients are to adhere to the visit schedule specified in the [Flow Chart](#). Each visit date (with its window) is to be counted from Day 1 (V1).

All deviations from the planned visit schedule are to be documented. If any visit has to be rescheduled, subsequent visits should follow the original visit date schedule. Additional visits for the purpose of retesting of laboratory parameters or AE monitoring may be included as deemed necessary by the investigator.

For detailed description of the trial procedures, please refer to the [Flow Chart](#).

Details relating to study drug administration and treatment interruptions are provided in [Section 4.1.4](#).

Study measurements and assessments are scheduled to occur 'before' trial medication administration. For planned individual plasma concentration sampling times refer to the [Flow Chart](#). Sampling times will be recorded and used for pharmacokinetic analysis.

6.2 DETAILS OF TRIAL PROCEDURES AT SELECTED VISITS

Study procedures to be performed at each visit are listed in the [Flow Chart](#) and respective sections of this protocol. Refer to [Section 5.1](#) for explanations of the specified assessments and procedural details.

The patients' questionnaires [REDACTED] are to be completed by the patient him/herself, without any help from or interpretation by other people. [REDACTED].

Separate from the PROs above, the evaluation of efficacy assessments (IGA, EASI, and SCORAD) are to be conducted preferably by the same qualified assessor, whenever possible, throughout the study.

The following procedures should be completed in the following order prior to trial drug administration:

- [REDACTED]
- [REDACTED]
3. IGA, EASI, SCORAD

6.2.1 Visit 1

For the comprehensive list of the trial procedures required at Visit 1 please refer to the [Flow Chart](#).

Visit 1 should preferably be performed in one visit combined with EOS visit of the preceding BI 655130 parent trial. These duplicate procedures across the two studies are performed only once when the visit is combined. When these two visits across both studies does not occur on the same day then all procedures will need to be performed at V1 of this trial. Refer to the [Flow Chart](#) for procedures that are identical across the two visits.

If a patient performs the EOS visit in the parent study but a newly observed medical finding (for example) prohibits the patient to immediately enrol into this study, the patient can come back for Visit 1 at a later date per the opinion of the investigator. The sponsor should be immediately notified if Visit 1 of this trial cannot be performed on the same day as the EOS in the parent study.

The maximum gap for enrolling into this trial is 12 weeks after the EOS in 1368-0032.

Informed Consent

After patients have been informed about the trial, written informed consent in accordance with GCP and the local legislation must be obtained prior to performing any study related procedures. Study requirements, including the procedure for the follow-up of prematurely withdrawn patients, must be fully explained to the patient. The importance of staying in the study until completion of all requirements is to be emphasized.

Once consent is obtained, the patient is to be recorded on the enrolment log. The informed consent date will be reported in the eCRF.

IRT procedures and administration of study drug

Once consent is obtained an initial “enrolment call” must be made in the IRT system. At that time a patient number will be generated.

When confirmed at Visit 1 that the patient meets all criteria and can be administered study medication, a medication assignment call must be made in the IRT system in order to dispense the first dose of study medication. Medication assignment via the IRT system and administration of study drug should be the last activity at Visit 1.

Details of IRT procedures can be found in the IRT manual located in the ISF.

Demographics:

The gender, ethnicity and race (if allowed by local law) will be collected and reported in the eCRF.

Medical History and Baseline Conditions:

Information on clinically significant previous and concomitant illnesses, other than AD, or any clinically significant signs or symptoms that are present before informed consent, or pre-existing conditions identified through findings from assessments and examinations done during Visit 1 will be recorded as medical and surgical history.

All ongoing AEs/SAEs at the end of the parent trial will be recorded on the Baseline Condition eCRF page of this 1368-0037 study.

Height and Weight

Height and Weight will be collected and reported in the eCRF per the [Flow Chart](#).

Smoking Status

Smoking status will be collected at and reported in the eCRF per the [Flow Chart](#).

Infection screening:

Infection testing will include tuberculosis, hepatitis B, hepatitis C, and HIV assessments (see [Table 5.2.3:1](#)). The results of the Infection Testing will not be available until after the patient receives the first dose at Visit 1. See [Section 3.3.4.1](#) for Discontinuation Rules.

If there is less than 12 week gap from the EOS of the preceding trial to V1 of this trial, the Infection testing does not have to be repeated at Visit 1.

QuantiFERON TB testing

Patients with suspected false positive or indeterminate QuantiFERON TB result may have the test repeated once. If after repeat testing the QuantiFERON TB result is “indeterminate” A PPD skin test may be performed locally. A tuberculin skin test reaction $\geq 10\text{mm}$ ($\geq 5\text{mm}$ if receiving $\geq 15\text{mg/d}$ prednisone or its equivalent) is considered positive.

Patients who now test positive for QuantiFERON TB test may continue and receive treatment in this study if further work up (according to local practice/guidelines) establishes conclusively that the patient has no evidence of active tuberculosis.

If presence of latent tuberculosis is established, patients can receive anti-tuberculosis treatment (according to local practice/guidelines) and continue receiving study medication.

Pregnancy Testing

Urine pregnancy testing for all woman of childbearing potential will be conducted on-site prior to every dosing and must be negative to receive study drug. A positive urine test must be confirmed with a serum pregnancy test at the central laboratory

Concomitant medication review:

Any concomitant treatment taken since the last visit of previous study will be recorded in the eCRF.

Review of inclusion/exclusion criteria:

Selection criteria will be reviewed carefully and patient eligibility confirmed prior to first dose.

Blood sampling

If EOS from the parent study and V1 from this study are performed on the same day, two lab kits will be required. The EOS lab kit from the parent study will be used. In addition a V1

lab kit from this trial will also need to be used as it contains labs not already included in the EOS from the previous parent trial. Details will be provided in the laboratory manual and the ISF.

For the comprehensive list of the trial procedures required at Visit 1 please refer to the [Flow Chart](#).

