2. V1 of this extension trial should be preferably performed during the EOS of the preceding BI 655130 parent trial. When the visits are performed on the same day duplicate procedures across studies are performed once during the EOS/V1. If these visits are not performed on the same day then all V1 procedures need to be performed at that visit. The only exception is Infection Testing which does not have to be repeated if performed at EOS of the parent trial and there is a <12 week gap from EOS of parent trial to V1 of this trial. Refer also to [Section 6.2.1](#)
3. After the individual patient's end of the trial the investigator should report only any cancers of new histology and exacerbations of existing cancer, study treatment related SAEs and study treatment related AESIs of which the investigator may become aware of and only via the BI SAE form. Refer to [Section 5.2.6.2.1](#).
4. All patients who receive at least one dose in the trial, including those who discontinue treatment prematurely, should complete the EOT visit as soon as possible and complete the EOS visit 16 weeks after the date of last trial drug administration.
5. Where possible, electrocardiogram (ECG) measurements should precede blood sampling and drug administration. Refer to [Section 5.2.4](#)
6. Body Surface Area (BSA) will be calculated from Part A of the SCORAD. All assessments must be done prior to trial drug administration. The questionnaires completed by patients should be done first before the investigator assessments. Refer to [Section 6.2](#)
7. Only applicable for women of childbearing potential. Urine pregnancy tests will be performed at all visits indicated in the [Flow Chart](#). Urine pregnancy testing should be done prior to administration of study drug. Study drug should only be administered in case of a negative test result. In case of a positive urine pregnancy test, a serum pregnancy test will be performed at the central laboratory.
8. Complete Physical Examination (PE) includes general appearance as well as evaluation of all organ systems.
9. Targeted physical examination includes evaluation of organ systems associated with AE(s) symptoms or laboratory abnormalities.
10. Vital signs will be assessed pre dose as well as within 1 hour post dose.
11. Safety laboratory tests include clinical chemistry, haematology, coagulation, and urinalysis, and will be performed centrally. Where possible, safety laboratory tests are to be drawn prior to dosing.

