12. Infection testing includes tuberculosis, hepatitis B, hepatitis C, and HIV assessments. Refer to [Table 5.2.3:1](#) and [Section 6.2.1](#). During a combined EOS/V1 only hepatitis C and HIV assessments will need to be done while results of tuberculosis and hepatitis B will be used from the parent trial.
13. At EOT visit, infection testing and ECG are only required if not done within the past 6 months.
14. 
15. For patients who complete the trial, the EOT visit will be the last treatment administration. For patients who discontinue early, there will be no treatment administration at the EOT visit.
16. There will be two IRT calls needed at Visit 1. The first is the study enrolment call performed after the patient signs consent; the second call is a "medication assignment" call performed after confirming eligibility to dispense the first dose of medication.
17. If a patient completes the trial and week 204 (Visit 52) is the EOT, then the site will need to make 2 IRT transactions- one transaction to dispense last medication, and another transaction to complete treatment. For patients who discontinue early, there will be 1 IRT call (transaction) to discontinue treatment.
18. Height is collected at Visit 1 only.

TABLE OF CONTENTS

TITLE PAGE	1
CLINICAL TRIAL PROTOCOL SYNOPSIS	2
FLOW CHART- YEAR 1	5
FLOW CHART- YEARS 2-4.....	6
FLOW CHART: END OF TREATMENT AND END OF STUDY VISITS	7
TABLE OF CONTENTS	9
ABBREVIATIONS	13
1. INTRODUCTION.....	16
1.1 MEDICAL BACKGROUND	16
1.2 DRUG PROFILE	17
1.2.1 Mode of Action	17
1.2.1.1 Residual Effect Period	17
1.2.1.2 Key pharmacokinetic characteristics	17
1.2.3 Clinical Experience	18
1.3 RATIONALE FOR PERFORMING THE TRIAL	19
1.4 BENEFIT - RISK ASSESSMENT.....	20
1.4.1 Benefits.....	20
1.4.2 Risks	20
1.4.3 Discussion.....	23
2. TRIAL OBJECTIVES AND ENDPOINTS.....	24
2.1 MAIN OBJECTIVES, PRIMARY AND SECONDARY ENDPOINTS.....	24
2.1.1 Main objectives.....	24
2.1.2 Primary endpoint	24
2.1.3 Secondary endpoints.....	24
3. DESCRIPTION OF DESIGN AND TRIAL POPULATION	26
3.1 OVERALL TRIAL DESIGN AND PLAN	26
3.2 DISCUSSION OF TRIAL DESIGN, INCLUDING THE CHOICE OF CONTROL GROUP(S)	27
3.3 SELECTION OF TRIAL POPULATION	27
3.3.1 Main diagnosis for trial entry	27
3.3.2 Inclusion criteria	28
3.3.3 Exclusion Criteria	29
3.3.4 Withdrawal of patients from treatment or assessments.....	29
3.3.4.1 Discontinuation of trial treatment	30
3.3.4.2 Withdrawal of consent to trial participation	31

3.3.4.3	Discontinuation of the trial by the sponsor	31

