Systemic Hypersensitivity	After administration of any biologic agent or protein there is a possibility of occurrence of adverse immune reactions which can be local (e.g. redness, pruritus, and or swelling at the injection site) or systemic (e.g. anaphylactic reactions). As patients have already been exposed in the parent trial, the risk of systemic hypersensitivity is low	Patients with a history of allergy/hypersensitivity to the systemically administered trial medication agent or its excipients are excluded from the trial. In case of systemic hypersensitivity reactions including anaphylactic reaction emerging during or after administration of trial medication, the investigator should consider in accordance with severity of the reaction and local standard of care (SoC) to interrupt and treat the condition. Systemic hypersensitivity reaction is defined as AESI. It is subject to close monitoring and investigators are requested assess these conditions using the criteria discussed in the statement paper from Sampson HA [R11-4890].
Infections	Inhibition of the immune response with an immune-modulating biologic may increase the risk of infections. A recent characterization of individuals with homozygous IL36R KO mutations revealed that normal immune function was broadly preserved suggesting that IL36 signaling pathway inhibition does not compromise host defenses	Screening procedures for infections will be established for this trial. Patients with any relevant chronic or active acute infections including human immunodeficiency virus (HIV), viral hepatitis or tuberculosis are excluded from the trial. Treatment of infections should be initiated promptly according to standards of care. Severe infections and opportunistic

	[R17-3632] .	
infections are considered AESI for this trial. These conditions and serious infections are subject to close monitoring.
 
Patients with active systemic infections during the parent 655130 study must delay Visit 1 in this study until the infection has resolved for at least 2 weeks.
 
An independent data monitoring committee (DMC) is in place to periodically evaluate clinical trial safety data.

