3.3.1 Main diagnosis for trial entry

Patients with AD will be included in this trial if they fulfil all the inclusion and do not present any of the exclusion criteria.

Patients who prematurely discontinued blinded treatment (up to Week 16) in the parent trial (1368-0032) are not eligible for this study. In addition patients from 1368-0032 must have

shown a response in order to be eligible. Patients from the 1368-0032 who were in the non-responder category at week 16, which was defined as less than EASI 75, must have completed the EOS visit and must attain at least an EASI 50 by the last infusion of BI 655130 (Week 28) or by the EOS in order to be eligible for this extension trial.

Patients from the 1368-0032 who were in the responder category at week 16 (V7) which was defined as an EASI 75 or greater, are eligible as long as they have completed the (EOS) visit. If this patient drops to an EASI 50 score prior to the planned EOS at Week 28, they will immediately perform EOS in 1368-0032 and enter into this extension trial.

Patients should enrol into the extension trial as soon as possible after conclusion of the parent trial. It is preferred that the end of study (EOS) visit from parent trial (1368-0032) will be combined with Visit 1 of this trial which includes the first SC dose of trial drug. The Sponsor must be notified if enrolment is delayed. Patients must be enrolled within a maximum of 12 weeks after the EOS visit from 1368-0032. (Refer to [Section 6.2.1](#) for more detailed information on study procedures).

The results of the safety labs as well as Infection Testing will be available/reported after the patient has entered and received the first dose of study medication in this trial. Refer to [Section 3.3.4.1](#) for discontinuation of treatment rules.

Please refer to [Section 8.3.1](#) (Source Documents) for the documentation requirements pertaining to the in- and exclusion criteria.

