3.3.3 Exclusion Criteria

1. Women who are pregnant, nursing, or who plan to become pregnant while in the trial. Refer to [Section 4.2.2.3](#)
2. Any new documented active or suspected malignancy except appropriately treated basal cell carcinoma, squamous cell carcinoma of the skin or in situ carcinoma of uterine cervix.
3. Use of any restricted medication as specified in [Section 4.2.2.1](#) or any drug considered likely to interfere with the safe conduct of the study, as assessed by the investigator.
4. Active systemic infections during the last two weeks prior to first drug administration. Refer to [Section 1.4.2](#) and [Section 4.2.1](#)
5. Currently enrolled in another investigational device or drug trial, except for 1368-0032.
6. Any condition which would prevent the patient continuing on treatment in this trial 1368-0037.
7. Evidence of a current or previous disease, medical condition (including chronic alcohol or drug abuse or any condition) other than AD, surgical procedure, psychiatric or social problems, medical examination finding (including vital signs and ECG), or laboratory value at the screening outside the reference range that in the opinion of the investigator is clinically significant and would make the study participant unreliable to adhere to the protocol, comply with all study visits/procedures or to complete the trial, compromise the safety of the patient or compromise the quality of the data.
8. History of allergy/hypersensitivity to the systemically administered trial medication agent or its excipients.

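### Section 6.2.1 waives infection testing at Visit 1 without the flow chart's conditions, and the risk table states an infection exclusion that the exclusion criteria do not name

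*Protocol*

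**What the plan says.** Four places in the protocol govern infection testing at entry.

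- **Section 6.2.1, infection screening.** The panel is defined first: "Infection testing will include tuberculosis, hepatitis B, hepatitis C, and HIV assessments". The waiver follows: "If there is less than 12 week gap from the EOS of the preceding trial to V1 of this trial", then "the Infection testing does not have to be repeated at Visit 1". It has no other condition.
- **Section 6.2.1, opening paragraphs.** When the parent EOS visit and Visit 1 fall on different days, the full set of Visit 1 procedures is required. No exception is mentioned. Entry is allowed up to 12 weeks after EOS.
- **Flow chart footnote 2.** Infection testing is the single exception to that rule. It "does not have to be repeated if performed at EOS of the parent trial" and the gap is under 12 weeks; both conditions must hold.
- **Flow chart footnote 12.** "During a combined EOS/V1 only hepatitis C and HIV assessments will need to be done"; tuberculosis and hepatitis B results are taken from the parent trial.

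On eligibility, the mitigation column of Table 1.4.2:1 says that patients with relevant chronic or active acute "infections including human immunodeficiency virus (HIV), viral hepatitis or tuberculosis are excluded from the trial". In Section 3.3.3 the only criterion that mentions infection is number 4: "Active systemic infections during the last two weeks prior to first drug administration". Section 3.3.1 says that infection test results "will be available/reported after the patient has entered and received the first dose of study medication". A positive HIV, hepatitis B or hepatitis C test and confirmed active tuberculosis appear in Section 3.3.4.1, as reasons to stop treatment.

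**The concern.** A site reading Section 6.2.1 alone sees a waiver of all four tests that depends only on elapsed time. A site reading the flow chart sees a waiver that also depends on what was tested at the parent EOS visit, and a specific instruction to test for hepatitis C and HIV at a combined visit. These do not lead to the same blood draw.

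The stake is patient safety at entry. The discontinuation rule for HIV and hepatitis can act only on a test result. If the test is skipped, nothing at entry can trigger the rule. The risk table meanwhile presents exclusion as the protection, so a reader of the benefit-risk section would believe that a barrier exists before the first dose. No endpoint or analysis depends on this point.

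**Working it through.** No figure in the plan needs reproducing. The check sets the passages side by side and adds two short counts.

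**1. Instructions by type of Visit 1**

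| Situation | Section 6.2.1 waiver | Section 6.2.1 opening | Footnote 2 | Footnote 12 |
|---|---|---|---|---|
| Combined EOS/V1 | Not clearly addressed | Duplicate procedures done once | Duplicate procedures done once | Hepatitis C and HIV required |
| Separate V1, gap under 12 weeks, panel done at EOS | No tests needed | All procedures | No tests needed | Silent |
| Separate V1, gap under 12 weeks, hepatitis C and HIV not done at EOS | No tests needed, read literally | All procedures | Waiver condition not met for these tests | Silent |
| Separate V1, gap exactly 12 weeks | Waiver does not apply | All procedures | Waiver does not apply | Silent |

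The third row is the clearest exposure: the waiver in 6.2.1 points one way, and footnote 2 and the opening of 6.2.1 point the other. It may well arise. Footnote 12 draws only tuberculosis and hepatitis B from the parent trial, which suggests that the parent EOS visit does not supply hepatitis C and HIV. That is an inference; the parent protocol is not among the documents.

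**2. Reach of the waiver among separate visits.** Permitted gaps run from 1 to 84 days (12 × 7 = 84). The waiver covers 1 to 83 days, so 83 of 84 permitted values. This counts permitted days, not patients; the distribution of actual gaps is not given.

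**3. Time to the next scheduled test if Visit 1 testing is skipped.** The Year 1 flow chart marks infection testing at V1 and V13 only, and dosing at every visit. V13 is Day 337: (337 − 1) / 28 = 12 intervals of four weeks. Doses before V13 are those at V1 to V12, that is, 12. A patient who stops earlier comes to the end-of-treatment visit, where footnote 13 requires infection testing if none was done in the past 6 months.

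**4. Exclusion in the risk table against the criteria**

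- HIV, viral hepatitis and tuberculosis are named in Table 1.4.2:1 but not in Section 3.3.3 or the synopsis.
- The first footnote to Table 5.2.3:1 lists Section 3.3.3, with the flow chart and Section 6.2.1, as a source of detail on infection testing. Section 3.3.3 contains none.
- Results of Visit 1 tests arrive after the first dose, so they cannot support exclusion before dosing.
- Section 6.2.1 lets patients with latent tuberculosis continue on study drug, while the risk table lists tuberculosis as excluded without that distinction.

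**The case against.** The strongest reply is that the flow chart and Section 6.2.1 can be read together. The restricted-medication section uses the word gap for the case where the two visits cannot share a day, and footnote 2 also places the waiver under separate visits. Footnote 12 then governs combined visits, and the two rules do not meet. To repeat a test presupposes that it was done, which is footnote 2's condition in other words. Section 6.2.1 refers the reader to the flow chart for the complete Visit 1 list. It also requires this trial's own Visit 1 laboratory kit at a combined visit, because that kit holds tests missing from the parent kit. On eligibility, criterion 6 (conditions that would stop a patient from staying on treatment), read with Section 3.3.4.1, would exclude a known positive, and criterion 7 could catch some others. The late arrival of results is disclosed twice, each time with a pointer to the discontinuation rules.

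Much of this stands. A reader might infer that 6.2.1 waives testing for nearly every patient, since entry is capped at 12 weeks. The documents do not support that: the inference treats a combined visit as a gap of zero, whereas the combined visit is the preferred route and footnote 12 with the Visit 1 kit covers it. A reader might also take twelve untested doses as the expected effect. That is a worst case, which requires a site to follow the 6.2.1 waiver and disregard the flow chart.

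What the reply does not remove is the separate visit. There the written waiver lacks footnote 2's condition, the same section asks for all procedures, and footnote 12 is silent. Nor do criteria 6 and 7 help with an infection that nobody has tested for.

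**Conclusion.** The inconsistency is real and limited. Section 6.2.1 omits a condition that footnote 2 states, conflicts with its own opening paragraphs for separate visits, and does not carry over footnote 12's requirement for combined visits. The exposure is a patient whose Visit 1 is separate, less than 12 weeks after EOS, without hepatitis C and HIV tests at EOS, at a site that takes 6.2.1 literally. For such a patient who stays on treatment, twelve doses precede the next scheduled test at Week 48. How many patients this describes cannot be derived from the documents.

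A reader might go further and conclude that patients could enter with no hepatitis C or HIV result at all. The documents do not show that: every patient comes from the parent trial, whose screening results are not given here. What can be said is that there might be no result from this trial or from the parent EOS visit.

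Separately, the exclusion stated in Table 1.4.2:1 has no named counterpart in Section 3.3.3. The safeguard that operates is the discontinuation rule in Section 3.3.4.1, acting after the first dose, with a separate provision for latent tuberculosis. Because both parts concern protection at entry, reconciliation is worth more than an editorial tidy-up.

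**What to change.** Reconcile Section 6.2.1 (both the opening paragraphs and the infection-screening paragraph), flow chart footnotes 2 and 12, Table 1.4.2:1, Section 3.3.3 and the cross-reference under Table 5.2.3:1. One list should state which infection tests are required at a combined Visit 1 and which at a separate one, with any condition on earlier results written out, and the other places should refer to it. The risk table should describe the safeguard that actually operates, including how latent tuberculosis is handled. Which tests are required, and whether these infections are grounds for exclusion or for stopping treatment, is the sponsor's clinical decision.

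The cost is protocol wording or a clarification letter to sites. The tests are already in the Visit 1 schedule. The one downside is that some sites may run tests that they now consider waived.
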